6.1.4. Handling of Dropouts or Missing Data

Although every attempt will be made to ensure participants remain in the study to completion and all data is collected as scheduled, the occurrence of missing data cannot be completely prevented.

An incomplete start or stop date of an AE or a medication will be imputed as described in section 6.1.8.

Any participant who withdraws from the study will be considered to have missing data at all subsequent visits. The primary analytic approach for efficacy assumes missing at random (MAR) to estimate what would have been observed if the participant had not discontinued. A reference-based multiple imputation sensitivity analysis (copy reference) will be employed in which missing not at random is assumed such that after discontinuation, drug-treated participants will have placebo-like values imputed for their missing data.

If up to two individual items of the total 12 items for the ADAS-Cog12 (maximum score = 80) are missing for non-cognitive reasons, the total score will be imputed by multiplying the observed score (i.e. the score for the non-missing items) by a factor that includes the maximum scores for the missing item(s) as follows:

$$\text{Imputed score} = \text{Observed score} * (80/[80-\text{maximum score for missing items}]).$$

As an example, if the first item “Word Recall” (maximum score = 10) and the second item “Commands” (maximum score = 5) are missing, the observed score will be multiplied by the factor $80/(80-[10+5])$ or $80/65$ or 1.23. The imputed score will be rounded to the nearest integer. ADAS-Cog12 tests with more than two missing items will be considered missing scores.

Missing items on other assessments will not be imputed; such scores will be considered missing.

6.1.5. Analysis Visit Windows

All scheduled visits and associated variables for the treatment phase will be analyzed based on the study week to which they are assigned.

For the safety summaries and analyses, scheduled analysis visits will be windowed to the nearest scheduled visit and the unscheduled visits/assessments and early termination visits will be mapped to a scheduled visit using the following visit windows (Table 2.1 and Table 2.2). Visit windows will be assigned by splitting the periods between visits at the mid-point between the visits.

If both scheduled and unscheduled visits fall within the same visit window, scheduled visit will be used over unscheduled visits. If both scheduled and early termination visits fall within the same visit window, the data from the early termination visit will supersede.

If more than one unscheduled visit falls within the same visit window, the one closest to the target date will be used in the analysis. If equidistant, the earliest visit will be used.

If the analysis visit (for Unscheduled or ET assessments) falls on a visit window in which that specific assessment is not scheduled, then that assessment will not be used for analysis.

Table 2.1: Visit Windows for Safety (Except for ECG) Analysis

Scheduled Visit	Scheduled Visit Day (Target Day)	Window for Assignment of Analysis Visit (Study Days ¹)
Week 4	Day 29	Day 2 – Day 71
Week 16	Day 113	Day 72 – Day 155
Week 28	Day 197	Day 156 – Day 239
Week 40	Day 281	Day 240 – Day 323
Week 52	Day 365	Day 324 – Day 407

¹Study Day relative to the date of first dose of study drug.

Table 2.2: Visit Windows for Safety (ECG only) Analysis

Scheduled Visit	Scheduled Visit Day (Target Day)	Window for Assignment of Analysis Visit (Study Days ¹)
Week 4	Day 29	Day 2 – Day 113
Week 28	Day 197	Day 114 – Day 281
Week 52	Day 365	Day 282 – Day 449

¹Study Day relative to the date of first dose of study drug.

For the efficacy summaries and analyses, scheduled analysis visits are visits upon scheduled time points as specified in the Schedule of Time and Events. Scheduled analysis visits will be windowed to the nearest scheduled visit. Assessments that fall within the same window will be averaged. There will be one valid value of assessment kept for each scheduled analysis visit in summary / analysis statistics.

Unscheduled visits are visits with data not collected at scheduled time points. Unscheduled visits will be windowed to the nearest scheduled visit as described above. All unscheduled visits will be included as collected in eCRF in listings.

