7.1.9. Unscheduled Visits and Discontinuation due to AEs

For unscheduled visits due to AEs, any assessments conducted will be at the discretion of the Investigator and pertinent to the AE. If a decision is made to discontinue the subject from Study Drug, the Sponsor will be notified immediately. The subject should be followed and treated by the Investigator until the AE has resolved or stabilized (see Section 10.1 – Adverse Events). Restarting the subject on Study Drug will be a mutual decision by the Investigator and the Sponsor. See also Section 9.0 – Early Discontinuation.

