This study is considered a registration study. Statistical tests will be regarded as formal tests of specific hypotheses.

The data from nominal/scheduled protocol clinic visits will be included in visit-based summary tables. Unscheduled assessments, if they occur, and the ET visit data will be mapped to scheduled assessments according to the visit windows defined in section 6.1.5 for all safety and efficacy analyses. See Section 6.1.4 and 6.1.5 of this SAP for more details.

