For partial end dates: (a) if only the day is missing, then the day is assigned the last day of the month; (b) if both day and month are missing, they are assigned the last day of the year (31DEC).

For analysis purposes, repeat laboratory results will not be used unless the original value is indicated as missing or invalid. In such cases, the first non-missing repeat value will be used for data analysis. The international system of units (SI) will be used in reporting all laboratory values.

Participants will be analyzed by the treatment received for all safety and tolerability assessments.

Participants are stratified through the IRT system based upon MMSE score entered. Once an MMSE score is entered, that participant is randomized to either high MMSE (21-27) or low MMSE (16-20) strata. At study start, it was decided to stratify participants in this manner so there would be a balance in the number of participants on placebo vs active drug (and within treatment arms) within each stratum. The stratification of the participants does not impact their probability of being assigned to different treatment arms. Once randomized through IRT, the MMSE score and the stratification assigned cannot be changed.

For instances where the MMSE score was incorrectly entered into IRT, the MMSE score given by the vendor will be used to calculate the strata for safety and efficacy analyses if there are any subgroup analyses.

All collected data will be presented in listings. Data not subject to analysis according to this plan will not appear in any tables or graphs but will be included only in the data listings.

A treatment related AE is any AE with a relationship to the study drug of *“Possibly Related”* or *“Probably Related”* or *“Reasonable Possibility”*.

If partial dates occur, the convention for replacing missing dates for the purpose of statistical analysis is as follows: if just day is missing then the day assigned is the first day of the month or the date of first dose (if in the same month), whichever is later; if just month is missing then the month assigned is the month of the first dose, unless that results in a date before the first dose in which case the month after the first dose is used; and if both month and day are missing then the month assigned is the month of the first dose and the day assigned is either the first day of the month or the first dose date, whichever is later.

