9.2.1. Stopping Criteria

Potential discontinuation of study drug for abnormal liver function tests should be considered if the study participant meets one or more of the following liver chemistry threshold stopping criteria:

- ALT or AST \geq 4x ULN;
- ALT or AST \geq 3x ULN and total bilirubin \geq 2x ULN;
- ALT or AST \geq 3x ULN if associated with the appearance or worsening of fatigue, nausea, vomiting, right upper quadrant pain or tenderness, fever, rash and/or eosinophilia;

or

- ALP elevations, if deemed of liver origin and drug-related as follows:
 - ALP > 3x ULN;
 - ALP > 2.5x ULN and total bilirubin > 2x ULN; or
 - ALP > 2.5x ULN if associated with the appearance or worsening of fatigue, nausea, vomiting, right upper quadrant pain or tenderness, fever, rash and/or eosinophilia,

where ULN = Upper Limit of Normal.

Study drug should be discontinued if a participant: (1) positively affirms suicidal ideation in response to questions number 4 or 5 in the suicidal ideation section of the C-SSRS, or (2) reports any suicidal behavior or non-suicidal self-injurious behavior since their last visit in response to the C-SSRS Suicidal Behavior questions.

Bodyweight loss (compared to weight at Baseline Visit [Study Day 1]) of \geq 2 kg resulting in a BMI < 18.5 is an additional stopping criterion.

Individual results of stopping criteria will be listed and summarized by presenting the number and percentage of participants who meet at least one post-dose stopping criteria.

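### The SAP's safety record-selection rules are not switched off for the stopping-criteria and QTc outlier counts, so a participant who met a laboratory, weight or QTc threshold only on an unselected record can be missing from the by-arm count

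*SAP*

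**What the plan says.** **Scope.** SAP 4.2 maps unscheduled and early-termination (ET) data to scheduled visits "according to the visit windows defined in section 6.1.5 for all safety and efficacy analyses".

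**Selection within a window (SAP 6.1.5, safety).** "If both scheduled and unscheduled visits fall within the same visit window, scheduled visit will be used over unscheduled visits". For the other overlap, "If both scheduled and early termination visits fall within the same visit window, the data from the early termination visit will supersede". Where several unscheduled visits share a window, the one nearest the target day is kept. None of these rules looks at how abnormal the value is.

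**Repeats (SAP 6.1.8).** For analysis, "repeat laboratory results will not be used unless the original value is indicated as missing or invalid".

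**The counts.** SAP 9.2.1 lists individual stopping-criteria results and summarises "the number and percentage of participants who meet at least one post-dose stopping criteria", which becomes Table 14.3.5.4. SAP 9.4 counts participants in categories of observed QT, QTcB and QTcF and of change from baseline (Tables 14.3.8.3 and 14.3.8.4). Neither section names the records that feed the count, and neither makes an exception to 6.1.5 or 6.1.8.

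**Where extra records come from.** Protocol 7.1.9 provides for unscheduled visits for adverse events, at which "any assessments conducted will be at the discretion of the Investigator and pertinent to the AE". Protocol 9 requires laboratory tests, weight and an ECG from subjects who leave the study early.

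**The concern.** A threshold count asks whether a participant ever crossed a line. A rule that keeps one representative record per window suits a by-visit mean but not that question, because the crossing may be on the record set aside. The extra records here (repeats, unscheduled draws, ET draws) are the ones a site collects when something looks abnormal.

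Table 14.3.5.4 is the only planned by-arm table that uses the liver thresholds. The laboratory shift tables classify against the normal range, and SAP 9.2 describes them as running from baseline to Week 52/ET/ED, so they do not replace it. Liver values deserve a reliable count: Protocol 2.2 reports adverse liver findings in the 6-month rat studies, with a 1.6-fold AUC margin at the NOAEL of the first. As the text stands, two programmers could also produce different counts from the same data.

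**Working it through.** **1. Reproduce the windows.** SAP 6.1.5 states: "Visit windows will be assigned by splitting the periods between visits at the mid-point between the visits". The target days are 29, 113, 197, 281 and 365.

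- Upper edges: (29+113)/2 = 71; (113+197)/2 = 155; (197+281)/2 = 239; (281+365)/2 = 323. Extending the last window by half an interval gives 365+42 = 407.
- This matches Table 2.1: Days 2-71, 72-155, 156-239, 240-323 and 324-407, with no gaps.
- ECG target days are 29, 197 and 365: (29+197)/2 = 113; (197+365)/2 = 281; 365+84 = 449. This matches Table 2.2.

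**2. How long a window stays open after the target day.**

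- Laboratory and weight: 71-29 = 155-113 = 239-197 = 323-281 = 407-365 = 42 days. With the protocol's visit allowance of 5 days either way, that is 37 to 47 days after the actual visit.
- ECG: 113-29 = 281-197 = 449-365 = 84 days.

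An ET visit within about six weeks of an abnormal scheduled laboratory visit therefore replaces it.

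**3. Apply the rules to hypothetical ALT series.** The values, in multiples of ULN, are assumed for illustration. The criterion is ALT at or above 4x ULN, and the window is Days 72-155 (target 113) unless noted.

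| Series | Ever met, all post-dose records | Counted under 6.1.5 and 6.1.8 |
|---|---|---|
| A. Scheduled Day 113: 4.5; ET Day 134: 1.5 | yes | no (ET replaces scheduled) |
| B. Scheduled Day 113: 2.8; unscheduled Day 127: 5.0 | yes | no (scheduled kept) |
| C. Original Day 113: 3.8; repeat Day 116: 4.6 | yes | no (repeat barred) |
| D. Unscheduled Day 127: 5.0; no scheduled visit in window | yes | yes |
| E. Scheduled Day 113: 4.5; ET Day 160: 1.5 (next window) | yes | yes |
| F. Original Day 113: 4.5; repeat Day 116: 2.0 | yes | yes |
| G. Unscheduled Day 75: 5.0 and Day 110: 1.2 | yes | no (Day 110 is 3 days from target, Day 75 is 38) |

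Four of the seven are not counted. The loss is conditional: it needs a competing record in the same window, or a valid original before the repeat. Four in seven describes these constructed cases and is not a rate expected in the trial.

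**4. Which counts are exposed.** The visit rules of 6.1.5 affect the laboratory and weight criteria and, through Table 2.2, the QTc categories. The repeat rule of 6.1.8 concerns laboratory results only.

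**5. Direction.** The selected records are a subset of all post-dose records, so each arm's selected count is at most its ever-met count. Let p be the true ever-met proportion in an arm and r the fraction of those participants who are captured. The observed difference is r_s x p_s - r_p x p_p (s = simufilam, p = placebo). If r_s = r_p = r, this is r x (p_s - p_p), a shrunken version of the true difference. If the capture fractions differ, the net effect can go either way. The documents give neither event rates nor capture fractions.

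**The case against.** The best defence is that 9.2.1 already means ever met. Its wording refers to at least one criterion after dosing, the table title names treatment but no visit, and SAP 4.2 introduces the window mapping while discussing visit-based tables. The explicit one-value-per-visit sentence in 6.1.5 stands in the efficacy paragraph; for safety it follows only from the tie-break rules. This reading is plausible, but it is not written. SAP 4.2 extends the mapping to all safety analyses, and where the SAP wants an any-time rule it states one, as for the C-SSRS composites in 9.7.

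The second defence is that nothing disappears. That is largely right. SAP 6.1.5 keeps unscheduled visits in listings, 9.2 lists all observed laboratory data with abnormal values flagged, and Listing 16.2.8.5 shows who met a criterion. Protocol 10.1 makes new clinically significant laboratory abnormalities adverse events, which reach the by-arm adverse event tables. But those tables are organised by coded term, not by threshold, and a listing is not a by-arm count.

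The third defence is that the rules ignore the value, so they do not systematically remove peaks. This stands. An ET draw can carry the peak and replace a normal scheduled value, and a high original is kept when its repeat is lower (series F).

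The C-SSRS criteria are a weak example, because 9.7 separately reports responses at any point. The point concerns laboratory, weight and QTc thresholds.

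**Conclusion.** The gap is real. Read literally, stated rules can give too low a participant count in Table 14.3.5.4 and in the categorical ECG tables, and nothing in 9.2.1 or 9.4 prevents it. Its size is unknown: the documents contain no event rates, and the worked series show only that the loss can happen. All safety summaries here are descriptive, so no formal test is affected.

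Three stronger conclusions might be inferred, and the documents do not support them.

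- **That the rules bias the comparison toward no difference.** This holds only if the drug raises the values and the capture fractions in the two arms are similar. Otherwise the net direction is undetermined.
- **That ET values are off-drug recovery values.** Protocol 9 ties the ET assessments to leaving the study and records the drug stop date separately. Protocol 7.1.10 has liver thresholds prompt consideration of stopping drug. An ET value after a liver-related stop may well be off drug, but no text says that it always is.
- **That qualifying cases vanish from the record.** No passage removes them from the listings.

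**What to change.** Add one sentence to SAP 9.2.1 and one to SAP 9.4. They should say that the stopping-criteria count, and any post-dose QTc outlier count, use every post-dose record (scheduled, unscheduled, repeat and ET), and that the record-selection rules of 6.1.5 and 6.1.8 apply only to by-visit summaries. Settle this before unblinding.

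The cost is two sentences and a small programming change. The one downside is that participants with more unscheduled draws have more chances to be counted; those draws are ordered by investigators blind to treatment. No change is needed to any clinical threshold, to the listings or to the by-visit means.

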2.2. Sample Size and Power

Planned enrollment was approximately seven hundred fifty (750) participants with mild-to-moderate AD dementia. The sample size was determined by a power analysis of ADAS-Cog using data from a similar population over 52 weeks. This analysis determined that group sizes of 300 are powered to show a 45% mean difference from placebo at 52 weeks with 90% power and a two-sided significance level of 0.05. The power calculation assumes a true mean change from baseline for placebo of 5.0 points and a standard deviation of 8.5 points. Assuming a drop-out of 20%, each treatment group should enroll approximately 375 participants. The final sample size was 804 randomized participants.

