3.2.1.2. Secondary Efficacy Endpoint(s) and Estimand(s)

The secondary efficacy endpoints of this study include the following:

- Mean change in the ADAS-Cog12 from baseline to Weeks 4, 16, 28 and 40
- Mean change in ADCS-ADL from baseline to Weeks 4, 16, 28 and 40
- Mean change in the iADRS (range 0 – 139, lower score indicates greater impairment) from baseline to Weeks 4, 16, 28, 40 and 52
- Mean change in the NPI-10 (range 0 – 120, higher score indicates greater impairment) from baseline to Weeks 28 and 52
- Mean change in the MMSE (range 0 – 30, lower score indicates greater impairment) from the screening visit to Weeks 28 and 52
- Mean change in the CDR-SB (range 0 – 18, higher score indicates greater impairment) from the screening visit to Week 52
- Mean change in the ZBI (range 0 – 88, higher score indicates greater caregiver burden) from baseline to Weeks 4, 16, 28, 40 and 52.

The estimands for the secondary efficacy endpoint(s) are similar to the co-primary estimands. Each secondary estimand has the following components:

Population	Participants with mild-to-moderate AD dementia who meet the study's inclusion and exclusion criteria.
Treatments	Simufilam 100 mg twice daily or placebo
Endpoints	ADAS-Cog12, ADCS-ADL, iADRS, NPI-10, MMSE, CDR-SB, ZBI
Summary Measure	Difference between treatments in LS mean change from baseline to the time points designated above
Intercurrent Events	All deviations from the intended dosing regimens and use of concomitant events medications will be handled consistently using a treatment policy strategy. Early study discontinuation will be consistently accounted for using a hypothetical strategy to estimate what would have been observed if the participant had not discontinued.

In addition, secondary estimands include the primary and secondary endpoints assessed in the population of participants with stage 4 AD. Stage 4 (mild) is defined as participants with baseline MMSE 21-27. Stage 4 and 5 represent all randomized participants.

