8.2. Secondary Efficacy Analysis

The iADRS, MMSE, NPI-10, and ZBI, in the ITT analysis set, and the ADAS-Cog12, ADCS-ADL, iADRS, MMSE, NPI-10, and ZBI, in the ITT-mild analysis set will be analyzed using the MMRM model as described for the primary analysis, with the exception for MMSE where the baseline value for the endpoint being analyzed is the MMSE baseline; therefore, the model for MMSE will include the categorical fixed effects of treatment group, Visit, and pooled site, along with the continuous, fixed covariate of baseline MMSE score and the interactions of treatment group and baseline MMSE with Visit.

The CDR-SB is only collected at Screening and Week 52. Therefore, the CDR-SB will be analyzed using ANCOVA with a model that includes treatment group, pooled site, and baseline MMSE. Plasma biomarkers will be analyzed with the MMRM analysis as described above.

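### CDR-SB scores taken at early termination are probably discarded, which leaves the second endpoint in the testing order as a complete-case ANCOVA with no missing-data method

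*SAP*

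**What the plan says.** - **Collection.** Protocol Section 9 requires CDR, MMSE and NPI at early discontinuation unless done in the previous 30 days. On CDR, SAP 8.2 states: "The CDR-SB is only collected at Screening and Week 52". Week 52 is therefore its only scheduled post-baseline visit.
- **Mapping of ET data.** SAP 4.2 states that "the ET visit data will be mapped to scheduled assessments according to the visit windows defined in section 6.1.5 for all safety and efficacy analyses".
- **Windows.** In SAP 6.1.5 the day ranges (Tables 2.1 and 2.2) are introduced for safety, and both tables are titled for safety. The same part says that if an unscheduled or ET assessment "falls on a visit window in which that specific assessment is not scheduled, then that assessment will not be used for analysis". The efficacy paragraph that follows reads "Scheduled analysis visits will be windowed to the nearest scheduled visit. Assessments that fall within the same window will be averaged". It gives no day ranges and does not mention ET.
- **Missing data.** SAP 6.1.4 treats a withdrawn participant as missing at all later visits and adopts missing at random (MAR) as the main efficacy approach. The copy-reference analysis in SAP 8.1.1 is specified for the co-primaries only.
- **Estimand.** For the secondary endpoints, SAP 3.2.1.2 states: "Early study discontinuation will be consistently accounted for using a hypothetical strategy to estimate what would have been observed".
- **Model and order.** SAP 8.2 analyses CDR-SB by ANCOVA with treatment, pooled site and baseline MMSE. SAP 6.1.3 tests it second, after iADRS and before ZBI, MMSE and NPI-10.

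**The concern.** A confirmatory endpoint needs one pre-specified dataset, and the efficacy text does not quite give one for CDR-SB. Two programmers could treat the same ET score differently.

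The larger matter lies behind the wording. If ET scores before Day 324 are dropped, nothing else carries those participants. There is no earlier CDR visit, no repeated-measures model and no imputation. The ANCOVA ignores the ET CDR-SB and any ADAS-Cog12 and ADCS-ADL decline seen before withdrawal. An MMRM under MAR uses the history of its own endpoint; this single-visit model has none to use. If withdrawal follows decline, the remaining sample is selected on outcome.

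CDR-SB decides whether ZBI, MMSE and NPI-10 can be formally tested. Its result in the full population also decides whether it is tested in the mild subgroup.

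**Working it through.** **1. The plan's own figure.** SAP 2.2 plans "with 90% power and a two-sided significance level of 0.05", and continues: "The power calculation assumes a true mean change from baseline for placebo of 5.0 points and a standard deviation of 8.5 points". The difference is 0.45 × 5.0 = 2.25 points. Then n = 2 × (1.960 + 1.282)² × 8.5² / 2.25² = 300 per group, with 90.0% power. On drop-out: "Assuming a drop-out of 20%, each treatment group should enroll approximately 375 participants". 300 / 0.80 = 375, so the figure reproduces. It concerns ADAS-Cog; the documents give no CDR-SB figure. Only the 20% drop-out and the final 804 randomized are used below.

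**2. Which rule governs an ET CDR-SB.**
- SAP 4.2 points to windows defined in 6.1.5. The only day ranges there are Table 2.1 and the ECG-only Table 2.2.
- A Day 60 assessment is 31 days from Week 4 (Day 29) and 53 from Week 16 (Day 113). Its nearest scheduled visit is Week 4, where CDR is not scheduled.
- SAP 6.1.4 makes the participant missing at later visits, which conflicts with calling that score Week 52.
- Labs, vital signs, weight, examinations and C-SSRS are scheduled at every post-baseline clinic visit, and the ECG windows are contiguous from Day 2 to Day 449. The dropping rule therefore has almost no work to do for safety. Among the scales collected at ET, it bites only on CDR, MMSE and NPI.

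These points favour dropping. The efficacy paragraph never says so.

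**3. Scores unused** (assuming withdrawal uniform over Days 2–365 and full ET attendance).
- Share before Day 324: 322 / 364 = 88.5%.
- Expected drop-outs: 0.20 × 804 = 160.8. Unused CDR-SB: 0.885 × 160.8 ≈ 142, or 142 / 804 = 17.7% of all randomized.
- The 142 is an upper figure; at half attendance it is about 71.
- MMSE and NPI-10: Days 156–239 (84 days) and 324–365 (42 days) give 126 / 364 = 34.6% usable.

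**4. Bias under dropping.** Simulation of 4,000 trials per scenario, 402 per arm, unadjusted difference in mean CDR-SB change (active minus placebo; positive is against active). Assumed, not in the documents: placebo decline D = 2.0 points, SD of change 2.5, linear decline. There is no true drug effect in the table. The last column uses within-arm regression imputation from ADAS-Cog12 visits only, so it shows bias, not error rate.

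| Drop-out (active/placebo) | Bias, dropping | Type I error | Bias, imputed |
|---|---|---|---|
| Random, 20%/20% | −0.004 | 4.9% | −0.005 |
| Random, 25%/15% | −0.002 | 4.7% | −0.002 |
| Decline-driven, both arms, 20%/20% | −0.003 | 5.2% | −0.004 |
| Decline-driven, both arms, 25%/15% | −0.060 | 6.3% | −0.004 |
| Decline-driven on placebo, random on active, 20%/20% | +0.135 | 11.5% | +0.002 |
| Same, driven by decline to Week 28 | +0.204 | 19.2% | +0.010 |
| Not at random on placebo, random on active, 20%/20% | +0.386 | 53.0% | +0.314 |

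With a true 45% effect (−0.90) and 20% drop-out per arm, dropping gave −0.901 under random and −0.897 under decline-driven drop-out in both arms.

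**5. If an ET score were instead labelled Week 52.** Bias = D × (1 − f) × difference in drop-out, with f = 0.5 of the year completed on average. For 25% active against 15% placebo: 2.0 × 0.5 × 0.10 = 0.10 in favour of active (simulated −0.099, type I error 9.1%). For D from 1.0 to 2.5 and a gap of 5 to 10 points, bias is 0.025 to 0.125 and type I error 5.2% to 10.9%. Equal 20% drop-out shrinks a true −0.90 to −0.81.

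**The case against.** The strongest reply is that the plan already settles the rule and that dropping is defensible. Much of this stands.

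- **Labelling.** A reader might infer that a Day 60 CDR-SB becomes the Week 52 value, by analogy with the ECG windows or because the schedule heads one column Week 52 ET/ED. The documents do not support this as the main reading. The ECG table is limited to ECG, the efficacy rule goes to the nearest visit rather than the nearest visit for that scale, and SAP 6.1.4 points the other way. Step 5 is therefore a reason to close the gap, not an expected result.
- **Bias either way.** A reader might also infer that CDR-SB is biased whichever rule applies. That is too strong. Dropping is unbiased under random drop-out and nearly so when mechanism and rate match across arms. The larger errors in step 4 need arms that differ, and the documents give no sign that they do.
- **Source.** Bias under dropping comes from the complete-case model rather than from the window rule alone.
- **Reach.** ADAS-Cog12, ADCS-ADL, iADRS and ZBI are available at every post-baseline visit. MMSE and NPI-10 keep Week 28 and the MMRM. CDR-SB is formally tested only after iADRS succeeds.
- **Remedy.** Multiple imputation is one choice among several.

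What the reply does not answer is that the plan states a hypothetical estimand and a MAR approach for efficacy, yet gives CDR-SB a model that uses no post-baseline information on those who leave, although such data are collected.

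**Conclusion.** The point holds as a should-fix matter. The likelier reading drops ET CDR-SB before Day 324, and the efficacy paragraph should say so. The resulting ANCOVA targets the stated estimand only if missingness depends on nothing beyond its covariates. Adding baseline CDR-SB, which SAP 6.1.2 implies and the list in 8.2 omits, does not change this, because it brings in no post-baseline decline.

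The bias is conditional and can favour either arm: from nil under random drop-out to −0.06 or about +0.14 to +0.20 points when drop-out follows observed decline and its mechanism or rate differs by arm. These sizes depend on the assumed CDR-SB decline, SD and drop-out pattern and are illustrative. The count of 142 of 161 depends on uniform timing, the planning drop-out rate and full ET attendance. Study success on the co-primaries is not at stake; the formal claims on CDR-SB and on the endpoints tested after it are.

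**What to change.** 1. **Window rule.** State in the efficacy paragraph of SAP 6.1.5 that the Table 2.1 windows and the dropping rule apply to ET efficacy data. No ET value before Day 324 then becomes Week 52 for CDR-SB, MMSE or NPI-10, and only Days 156–239 count as Week 28 for MMSE and NPI-10. Those two scales need nothing more.
2. **CDR-SB.** In SAP 8.2, impute missing Week 52 CDR-SB by multiple imputation under MAR within arm. Use baseline CDR-SB, baseline MMSE and the observed ADAS-Cog12 and ADCS-ADL visits. Run the ANCOVA on all ITT participants and combine by Rubin's rules. Where an ET CDR-SB exists, it can be added with its study day. Completers have no mid-study CDR to match it, so this needs an imputation model with time in it.

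The cost is SAP wording and one more imputation program; all inputs are already collected. The method does not remove bias when drop-out depends on unobserved outcomes (+0.314 against +0.386 in the last scenario). Both changes should be made before unblinding.
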